6.6.2 Adverse Events

An AE is defined per protocol as any new untoward medical occurrence or worsening of a preexisting medical condition in a patient or clinical investigation participant administered an investigational (medicinal) product and that does not necessarily have a causal relationship with this treatment. An AE can therefore be any unfavorable and unintended sign (including an abnormal laboratory finding, for example), symptom, or disease temporally associated with the use of investigational product, whether or not considered related to the investigational product. AEs can be spontaneously reported or elicited during open-ended questioning, examination, or evaluation of a participant.

Verbatim terms are coded and grouped by system organ class using the latest version of the Medical Dictionary for Regulatory Activities (MedDRA) in production at BMS. Investigators determine the intensity of AEs (mild [Grade 1], moderate [Grade 2], severe [Grade 3], very severe [Grade 4]), and determine the relationship of AEs to study therapy (related, not related).

In order to account for AEs with multiple occurrences in the same participant, AE records are collapsed for each participant and preferred term when records have the same onset date, or when records are contiguous or overlapping ¹⁰. All AE presentations are based on collapsed records.

AEs are summarized as categorical parameters by system organ class (SOC) and preferred term, both in descending order of total frequency. Summaries include both non-SAEs and SAEs, unless otherwise specified.

AE summaries separately by analysis period are presented in Table 6.6.2-1.

Table 6.6.2-1: AE Summaries by Analysis Period

Endpoint	On-Treatment	Follow-up
SAEs	X	X
AEs leading to discontinuation of study therapy	X	
AEs by intensity or relationship: All Grades; Grade 3 to 4; All Grades related to study therapy (on-treatment only)	X	X
Non-SAEs $\geq 5\%$ ^{a,b}	X	
Exposure-adjusted multiple SAEs ^a	X	
Exposure-adjusted multiple SAEs related to study therapy ^a	X	

Table 6.6.2-1: AE Summaries by Analysis Period

Endpoint	On-Treatment	Follow-up
Exposure-adjusted multiple non-SAEs $\geq 5\%^{a,b}$	X	

^a ClinicalTrials.gov or EudraCT reporting requirement

A by-participant listing of all AEs is provided for enrolled participants.

6.6.2.1 AEs by Intensity or Relationship to Study Therapy

For graded summaries of AEs (e.g., AEs by intensity, AEs by relationship), AEs with missing intensity are included only in summaries of All Grades events. The greatest intensity during a safety analysis period is presented for each AE.

AEs related to study therapy are those with a "related" or missing relationship to the study therapy. If relatedness to study therapy is unknown, the AE is included in summaries of AEs judged by the investigator to be related to study therapy.

6.6.2.2 Exposure-Adjusted Multiple AEs

Analyses take into account the number of occurrences of an AE reported by individual participants and their cumulative exposure on treatment. These data are presented as the rate per 100 years of patient exposure. For example, if 5 participants report 7 unique episodes of headache and had a combined cumulative exposure of 20 years to study medication, the incidence rate is reported as 7/20 *(100) or 35 cases per 100 patient years of exposure.

Cumulative exposure is defined as (1) time on study therapy for participants who have not discontinued study therapy, and (2) time on study therapy + 7 days for participants who discontinued study therapy to account for on-treatment safety reporting.

6.6.3 Hepatic Disease Progression

Hepatic disease progression is summarized by the categories specified in Table 6.6.3-1 during the on-treatment and follow-up analysis periods combined for treated participants. Hepatic disease progression is identified from the Hepatic Related Diagnoses CRF.

Table 6.6.3-1: Hepatic Disease Progression Diagnoses

Diagnoses

Cirrhosis, non-bleeding esophageal varices, bleeding esophageal varices, hepatic encephalopathy, hepatocellular carcinoma, spontaneous bacterial peritonitis, non-bleeding gastric varices, bleeding gastric varices, hepatorenal syndrome, liver transplant

A by-participant listing of hepatic disease progression is provided for enrolled participants.

b Cut-off applies to frequency of participants with preferred terms in any cohort.

6.6.4 Clinical Laboratory Evaluations

Summaries are based on treated participants with at least one laboratory measurement during the analysis period. All output is presented separately for SI and US units.

EOT toxicity grades and values are determined form the last laboratory test value collected during the on-treatment analysis period.

End of study (EOS) toxicity grades and values are determined form the last laboratory test value collected during the follow-up analysis period.

By-participant listings are provided for enrolled participants for the following laboratory tests:

- Hematology: hematocrit, hemoglobin, platelets, INR, WBC, lymphocytes (absolute), and ANC;
- Hepatobiliary enzymes and measures of hepatic synthetic function: ALT, AST, AST to platelet ratio index (APRI), alkaline phosphatase, total bilirubin, albumin, and alpha fetoprotein;
- Pancreatic enzymes and renal function tests: lipase (colorimetric or turbidimetric), creatinine, and creatinine clearance using the Schwartz formula;
- Electrolytes: bicarbonate, calcium, phosphate, potassium, and sodium.

These listings identify laboratory abnormalities using toxicity grades as specified in Section 6.3.2.4.

6.6.4.1 Laboratory Abnormalities by Toxicity Grade

Laboratory abnormalities are summarized by analysis period (on-treatment and follow-up) in the following toxicity grade categories:

- Worst toxicity grade: 0, 1, 2, 3, 4, 3 to 4, 1 to 4;
- Worst emergent toxicity grade: not emergent, 1, 2, 3, 4, 3 to 4, 1 to 4.

See Section 6.3.2.4 for laboratory tests with toxicity grades. Electrolytes are excluded from summaries due to infrequent post-baseline testing.

Emergent abnormalities on treatment are laboratory tests on treatment that have a higher toxicity grade than the baseline toxicity grade (including missing baseline). The category "not emergent" represents laboratory tests on treatment that have the same or lower toxicity grade than the baseline toxicity grade.

Emergent abnormalities during follow-up are laboratory tests during follow-up that have a higher toxicity grade than the EOT toxicity grade (including missing EOT). The category "not emergent" represents laboratory tests during follow-up that have the same or lower toxicity grade than the EOT toxicity grade.

The laboratory value during the analysis period with the worst (highest) toxicity grade is reported for each laboratory test.

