4 OBJECTIVES AND ENDPOINTS

Table 4-1: Objectives and Endpoints

Note: With the early termination of this study, previously collected data to address PK, SVR, and select safety assessments (e.g. AEs, laboratory tests, end of treatment subject status) will be reported only within adolescent participants 12 to <18 years of age. The secondary objectives related to assessment of genotypic substitutions associated with virologic failure and the acceptability and palatability of the daclatasvir formulations and the exploratory objective regarding durability of response will not be reported.

Objectives	Endpoints

Primary
 
 To evaluate the PK profile of DCV in combination with SOF in children and adolescents aged 3 to <18 years of age 	
 Pharmacokinetic parameters (C_{min}, C_{max}, T_{max}, AUC (TAU), CLT/F) for DCV derived from plasma concentration versus time data on Day 10 (± 3 days) within a dosing interval. In Cohort 3 (ages 3 to < 6 years of age); PK parameters will be assessed using model-based analyses with 5 samples from each participant.

Secondary
 
 To assess the safety and tolerability of the DCV+SOF regimen in paediatric participants 	
 Frequencies of serious adverse events (SAEs), adverse events (AEs) leading to discontinuation of study therapy, AEs by intensity, and laboratory abnormalities by toxicity grade on treatment and during follow-up

 To determine the proportion of participants with SVR12 	
 Proportion of participants with HCV RNA <LLOQ (TD or TND) at post-treatment follow-up Week 12

 To evaluate genotypic substitution(s) associated with virologic failure 	
 Frequencies of NS5A and NS5B resistance-associated variants (RAVs) emergent at the time of virologic failure on treatment and during follow-up in non-responders

 To assess the acceptability and palatability for the age-appropriate chewable tablet formulation, and acceptability for adult film-coated tablet 	
 Summary of responses from questionnaire assessing acceptability and palatability at Day 1, Week 4, and Week 12

[REDACTED]
	
[REDACTED]

[REDACTED]
	
[REDACTED]

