9.4.4 Clinical Safety Laboratory Assessments

- Investigators must document their review of each laboratory safety report.
- The following assessments, listed in Table 9.4.4-1, will be analyzed by a central laboratory or other BMS specified laboratory.
- Participants are not required to be fasting prior to any laboratory assessments.

	Screening (Table 2-1)	Study Visits On Treatment (Table 2-2)	Study Visit Post-Treatment Week 4 (Table 2-3)	Study Visits Post-Treatment Weeks 12 to 108 (Table 2-3)
Hematology				
Hemoglobin	X	X	X	-
Hematocrit	X	X	X	-
White Blood Cell (WBC) Count with Differential	X	X	X	-
ANC (neutrophils plus band)	X	X	X	-
Platelets	X	X	X	X
Coagulation				
INR	X	X Not required Day 10	X	X
Chemistry				
Albumin	X	X	X	X
Total Protein	X	X	X	-
Aspartate aminotransferase (AST)	X	X	X	X
Alanine aminotransferase (ALT)	X	X	X	X
Total bilirubin	X	X	X	X
Direct Bilirubin	X	X	X	X
Alkaline Phosphatase	X	X	X	X
Lactate dehydrogenase (LDH)	X	X	X	X
Creatinine	X	X	X	X
Creatinine Clearance	X	X	X	X

Table 9.4.4-1: Laboratory Assessments				
	Screening (Table 2-1)	Study Visits On Treatment (Table 2-2)	Study Visit Post-Treatment Week 4 (Table 2-3)	Study Visits Post-Treatment Weeks 12 to 108 (Table 2-3)
Creatinine phosphokinase (CPK)	-	For AST elevation ≥ Grade 1 without ALT elevation		
Creatine Kinase MB Isoenzyme (CK-MB)	-	Reflex if CPK is elevated > 5xULN		
Lipase	X	X	X	-
Gamma-Glutamyl Transferase (GGT)	X	X	X	X
Electrolytes (sodium, bicarbonate, potassium, chloride)	X	-	X	-
Blood Urea Nitrogen (BUN)	X	-	X	-
Glucose	X	-	X	-
HbA1c	X Only in participant with elevated plasma glucose level ≥ 200 mg/dL (11.1 mmol/L)	-	X	-
Calcium	X	-	X	-
Phosphate	X	-	X	-
Uric Acid	X	-	X	-
Alfa fetoprotein (AFP)	X	-	X	-
APRI	X	-	X	X Week 108 only
Other				
Urine pregnancy test (reflex to serum if positive)	X 24 hours prior to dosing in FOCBP	X Every 4 weeks	X	-
HCV RNA (and back up HCV RNA sample)	X	X	X	X
HCV resistance specimen for storage	-	X	X	X

Table 9.4.4-1: Laboratory Assessments				
	Screening (Table 2-1)	Study Visits On Treatment (Table 2-2)	Study Visit Post-Treatment Week 4 (Table 2-3)	Study Visits Post-Treatment Weeks 12 to 108 (Table 2-3)
HCV genotype	X	Participants with suspected virologic breakthrough or relapse will have samples collected to retest HCV RNA, HCV resistance and HCV Genotype at an unscheduled visit as soon as possible before their next regular visit.		
Anti-HCV	X	-	-	-
HIV-1 and -2 antibody	X	-	-	-
HBsAg, anti-HBcore	X	-	-	-
	-	X (Day 1 only)	-	-

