10.3.3 Safety Analyses

The frequencies of the following safety endpoints will be presented separately for each study period (on treatment and follow-up) for treated participants by age cohort and total: SAEs; AEs leading to discontinuation of study therapy; AEs by intensity; laboratory abnormalities by toxicity grade.

The Investigators will determine the intensity of AEs. The Investigators' terms will be coded and grouped by system organ class using the latest version of the Medical Dictionary for Regulatory Activities (MedDRA) in production. AEs will be presented by system organ class and preferred term. Presentations will include both non-serious and SAEs, unless specified otherwise. If a participant had an AE with different intensities over time, then only the greatest intensity will be reported for a study period.

Laboratory toxicities will be graded according to the Division of AIDS (DAIDS) of the US National Institutes of Health table for grading the severity of adverse experiences ([December 2004; clarification August 2009]) ([Appendix 5](#)). The laboratory value during the study period with the highest toxicity grade will be reported for each test.

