< 7 days of age	11.5 to < 12.4 2.88 to < 3.10	12.4 to < 12.9 3.10 to < 3.23	12.9 to < 13.5 3.23 to < 3.38	≥ 13.5 ≥ 3.38
Calcium (Ionized), High (mg/dL; mmol/L)	> ULN to < 6.0 > ULN to < 1.5	6.0 to < 6.4 1.5 to < 1.6	6.4 to < 7.2 1.6 to < 1.8	≥ 7.2 ≥ 1.8
Calcium, Low (mg/dL; mmol/L) ≥ 7 days of age	7.8 to < 8.4 1.95 to < 2.10	7.0 to < 7.8 1.75 to < 1.95	6.1 to < 7.0 1.53 to < 1.75	< 6.1 < 1.53
< 7 days of age	6.5 to < 7.5 1.63 to < 1.88	6.0 to < 6.5 1.50 to < 1.63	5.50 to < 6.0 1.38 to < 1.50	< 5.50 < 1.38
Calcium (Ionized), Low (mg/dL; mmol/L)	< LLN to 4.0 < LLN to 1.0	3.6 to < 4.0 0.9 to < 1.0	3.2 to < 3.6 0.8 to < 0.9	< 3.2 < 0.8
Cardiac Troponin I, High	NA	NA	NA	Levels consistent with myocardial infarction or unstable angina as defined by the local laboratory
Creatine Kinase, High	3 to < 6 x ULN	6 to < 10x ULN	10 to < 20 x ULN	≥ 20 x ULN
Creatinine, High *Report only one	1.1 to 1.3 x ULN	> 1.3 to 1.8 x ULN OR Increase to 1.3 to < 1.5 x participant's baseline	> 1.8 to < 3.5 x ULN OR Increase to 1.5 to < 2.0 x participant's baseline	≥ 3.5 x ULN OR Increase of ≥ 2.0 x participant's baseline
Creatinine Clearance¹⁴ or eGFR, Low *Report only one	NA	< 90 to 60 ml/min or ml/min/1.73 m ² OR 10 to < 30% decrease from participant's baseline	< 60 to 30 ml/min or ml/min/1.73 m ² OR 30 to < 50% decrease from participant's baseline	< 30 ml/min or ml/min/1.73 m ² OR ≥ 50% decrease from participant's baseline or dialysis needed
Glucose (mg/dL; mmol/L) Fasting, High	110 to 125 6.11 to < 6.95	> 125 to 250 6.95 to < 13.89	> 250 to 500 13.89 to < 27.75	≥ 500 ≥ 27.75
Nonfasting, High	116 to 160 6.44 to < 8.89	> 160 to 250 8.89 to < 13.89	> 250 to 500 13.89 to < 27.75	≥ 500 ≥ 27.75

¹⁴ Use the applicable formula (i.e., Cockcroft-Gault in mL/min or Schwartz, MDRD, CKD-Epi in mL/min/1.73m²). Sites should choose the method defined in their study and when not specified, use the method most relevant to the study population.

*Reminder: Choose the method that selects for the higher grade.

Chemistries

PARAMETER	GRADE 1 MILD	GRADE 2 MODERATE	GRADE 3 SEVERE	GRADE 4 POTENTIALLY LIFE- THREATENING
Glucose, Low (mg/dL; mmol/L) ≥ 1 month of age	55 to 64 3.05 to <3.55	40 to < 55 2.22 to < 3.05	30 to < 40 1.67 to < 2.22	< 30 < 1.67
< 1 month of age	50 to 54 2.78 to < 3.00	40 to < 50 2.22 to < 2.78	30 to < 40 1.67 to < 2.22	< 30 < 1.67

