6.3.2.4 Laboratory Tests at Baseline

Laboratory test abnormalities at baseline are summarized as categorical parameters using toxicity grades separately for SI and US units. Percentages are based on participants with measurements.

Commonly collected laboratory tests that are graded using the Division of AIDS (DAIDS) Table for Grading the Severity of Adult and Pediatric Adverse Events (2004)⁴ toxicity grades (Grades 0, 1, 2, 3, 4; Grade 1 to 4; Grade 3 to 4) include the following, as applicable:

- Hematology: hemoglobin, platelets, international normalized ratio (INR), white blood cell count (WBC), lymphocytes (absolute; only for Cohort 1 participants > 13 years old), and neutrophils + bands (absolute; ANC);
- Hepatobiliary enzymes and measures of hepatic synthetic function: alanine aminotransferase (ALT), aspartate aminotransferase (AST), alkaline phosphatase, total bilirubin, and albumin;
- Pancreatic enzymes and renal function tests: lipase (colorimetric or turbidimetric) and creatinine;
- Electrolytes: bicarbonate (low), calcium (high and low), phosphate (low), potassium (high and low), and sodium (high and low).

See Protocol Appendix 5 for DAIDS toxicity grades.

In the absence of DAIDS toxicity grades, the following toxicity grade categories are provided for creatinine clearance using the Schwartz formula:

- SI units (mL/s/ m^2): < 0.25 (Grade 4); 0.25 to < 0.50 (Grade 3); 0.50 to < 1.0 (Grade 2); 1.0 to < 1.5 (Grade 1); \ge 1.5 (Grade 0);
- US units (mL/min/1.73 m²): < 15 (Grade 4); 15 to < 30 (Grade 3); 30 to < 60 (Grade 2); 60 to < 90 (Grade 1); ≥ 90 (Grade 0).

General Medical History

A by-participant listing of general medical history is provided for enrolled participants.

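### Glucose, uric acid and reflex CPK appear in no SAP laboratory output, and electrolytes are missing from the follow-up worst-grade table, although protocol and SAP promise the worst grade for every test

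*SAP*

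**What the plan says.** The secondary safety endpoint in Protocol Section 4 includes "laboratory abnormalities by toxicity grade on treatment and during follow-up". Protocol 10.3.3 sets the reporting rule and exempts no test: "The laboratory value during the study period with the highest toxicity grade will be reported for each test".

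SAP 6.6.4.1 repeats the rule for its own analysis periods: "The laboratory value during the analysis period with the worst (highest) toxicity grade is reported for each laboratory test". In the same section it states: "Electrolytes are excluded from summaries due to infrequent post-baseline testing". The tests eligible for these tables are those in the graded list of SAP 6.3.2.4. Under electrolytes that list includes calcium and phosphate as well as sodium, potassium and bicarbonate.

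The by-participant listings in SAP 6.6.4 keep this group ("Electrolytes: bicarbonate, calcium, phosphate, potassium, and sodium") and carry toxicity grades.

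On collection, Protocol Table 9.4.4-1 has electrolytes, calcium, phosphate, glucose and uric acid at screening and Post-Treatment Week 4 only. CPK has no fixed visit and is a reflex test after screening: "For AST elevation ≥ Grade 1 without ALT elevation". The chemistry table in Protocol Appendix 5 gives grades for non-fasting and low glucose, uric acid and "Creatine Kinase, High".

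The early-termination note in Protocol 10.3 keeps laboratory tests among the safety data to be reported, for 5 participants, and rules out statistical analyses.

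**The concern.** The SAP departs from the protocol's rule, and from its own restatement of that rule, in two ways.

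First, three tests that are collected and gradable have no place in any laboratory output. The laboratory endpoint is meant to record a measured grade whether or not an investigator thought the result important. If the only route into the report is an adverse event entry, the endpoint for these tests depends on that judgement, and a reader of the laboratory section cannot tell a normal result from one that was never shown.

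Second, the electrolyte exclusion applies to both post-baseline periods, although its reason has real force in only one of them. A graded electrolyte abnormality at Post-Treatment Week 4 would be absent from the table that summarises the follow-up part of the endpoint.

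**Working it through.** No power or sample size figure is involved. The check compares what is collected and graded with what the SAP outputs.

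**Step 1. Scheduled tests after Day 1, per participant, under the full schedule.** Inputs are Protocol Tables 2-2, 2-3 and 9.4.4-1.
- On-treatment visits after Day 1: Day 10 and Weeks 4, 8 and 12, which is 4.
- Follow-up visits: Post-Treatment Weeks 4, 12, 24, 48, 72, 96 and 108, which is 7.
- ALT: 4 + 7 = 11.
- Haemoglobin, WBC, ANC and lipase: 4 + 1 = 5. The one follow-up visit is Post-Treatment Week 4.
- Electrolytes, calcium, phosphate, glucose and uric acid: 0 + 1 = 1, at that same visit.
- CPK: no fixed number.

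**Step 2. Where each test appears in the SAP.**

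| Test | On treatment | Follow-up | Baseline grades (6.3.2.4) | Post-baseline grade tables (6.6.4.1) | Graded listing (6.6.4) |
|---|---|---|---|---|---|
| ALT | 4 | 7 | yes | yes | yes |
| Haemoglobin, WBC, ANC, lipase | 4 | 1 | yes | yes | yes |
| Sodium, potassium, bicarbonate, calcium, phosphate | 0 | 1 | yes | no | yes |
| Glucose, uric acid | 0 | 1 | no | no | no |
| CPK | reflex | reflex | no | no | no |

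The change-over-time tables (6.6.4.2) and the select results (6.6.4.3) name none of the tests in the last three rows. Electrolytes are therefore in two SAP laboratory outputs, both outside the post-baseline summaries. Glucose, uric acid and CPK are in none.

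**Step 3. Does infrequent testing separate what is dropped from what is kept?** On treatment it does: 0 scheduled tests against 4. In follow-up it does not: rows 2 and 3 both have 1 scheduled test, at the same visit, and only row 2 is tabulated.

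**Step 4. What would happen if the exclusion were simply deleted?** SAP 6.6.4.1 judges follow-up emergence against the end-of-treatment grade and counts a missing end-of-treatment grade as emergent. Take a participant with Grade 1 glucose at screening and Grade 1 at Post-Treatment Week 4. There is no scheduled on-treatment value, so the end-of-treatment grade is missing and the unchanged result is classed as emergent. Against baseline it is not emergent. The same applies to uric acid and electrolytes. CPK has no scheduled screening value either, so a baseline comparator would not generally help there.

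**The case against.** The best case for the SAP has four parts.

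**The stated reason is true.** One scheduled post-baseline test, with none on treatment, is infrequent. Haemoglobin and the other retained tests also have an end-of-treatment value, which the emergent-grade table needs. This stands for the on-treatment table and for the emergent table. It does not explain the omission from the follow-up worst-grade table, which needs no comparator.

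**Electrolytes are not lost.** A reader might infer that a severe electrolyte result would vanish from the report. The documents do not support that: SAP 6.6.4 lists these tests by participant with grades, and with 5 participants such a listing shows every value. For electrolytes the gap is in the summary only.

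**Other routes exist.** Protocol 9.2.6 sends results to the adverse event pages if they are clinically significant, meet the serious-event definition, or lead to corrective therapy or to treatment being stopped or interrupted. Protocol 9.4.4 requires documented review of each laboratory report. These lower the risk but rest on judgement or action, whereas the endpoint rests on the grade. SAP 6.3.2.4 also describes its graded list with an as-applicable qualifier, which leaves some room. The listing section names a fixed set without the three tests.

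**Early termination reduces the stakes.** The note in Protocol 10.3 confines reporting to selected safety assessments and may leave no frequency tables at all. That stands, and it makes the listings the output that matters most.

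It is also tempting to state the gap as a share of graded parameters, or as the percentage effect of one missed participant. Neither is secure. The share changes with counting by test or by direction, and with whether direct bilirubin is included; that test is collected and graded in Appendix 5 but is also absent from the SAP lists. The SAP cites the 2004 grading table while pointing to Appendix 5, which is the July 2017 version. A participant percentage presumes a frequency table that may not be produced.

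**Conclusion.** The point holds at modest weight. Three tests with Appendix 5 grades (glucose, uric acid and CPK) have no SAP laboratory output, contrary to the every-test rule in both documents. Five electrolyte analytes are missing from the follow-up worst-grade summary for a reason that applies equally to four retained tests in that period. They remain visible in graded listings.

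The affected data are essentially one follow-up visit per participant plus any reflex CPK, in 5 participants, so the practical effect is small. It is still worth correcting, because the endpoint is a stated one and the data already exist.

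The conclusion assumes that grading follows Protocol Appendix 5 as printed, and that the SAP lists are meant to be complete as written. It does not depend on any such abnormality having occurred; the documents do not say whether one did.

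**What to change.** 1. Add glucose (non-fasting high, and low), uric acid and CPK to the graded list in SAP 6.3.2.4 and to the by-participant listings in SAP 6.6.4. Label CPK as tested by reflex only. This is the minimum needed.
2. In SAP 6.6.4.1, limit the electrolyte exclusion to the on-treatment table and extend it to glucose and uric acid, which also have no scheduled on-treatment test. Show electrolytes, calcium, phosphate, glucose and uric acid in the follow-up worst-grade table with the number of participants measured.
3. For tests without a scheduled on-treatment value, define follow-up emergence against baseline instead of end of treatment, or leave them out of the emergent-grade table. For CPK, leaving it out is the workable choice, since no baseline is scheduled. If CPK worst grades are tabulated, give the number tested and a footnote on selective testing.

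If early termination means that only listings are produced, step 1 is enough.

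The cost is a short SAP edit and a few rows in existing table and listing programs, with no new data. The downsides are denominators from a single visit and a CPK row that describes a selected subset.
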